# Funding Body

Applications under review.

# STUDY SYNOPSIS

Title of Study:	Defining the Denominator: Emergency Laparotomy and Frailty Study 2.	
Study Centre:	Multicentre	
Duration of Study:	25 months	
Primary Objective:	Identify a U.K. consecutive series of older adults presenting with acute abdominal pathology potentially treatable by emergency laparotomy where the decision is made not to undergo surgery (NoLAP) and their associated 90- day mortality.	
Secondary Objective:	Collect, define and characterise the reasoning behind the NOLAP decision.	
Primary Endpoint:	Characterise NoLAP patient populations and document 90-day mortality.	
Rationale:	Older patients that require, but do not undergo emergency laparotomy (NoLAP) are an undefined and uncharacterised population. In contrast to those older adults that undergo emergency surgery, it is not known how many patients constitute this NoLAP group, what characteristics they have, what the reasons are for not undergoing surgery and what their short-term outcomes are.	
Methodology:	Prospective cohort study	
Sample Size:	700	
Screening:	n/a	
Registration/ Randomisation:	Via REDCap database.	
Main Inclusion Criteria:	
 
65 years or older
 
requires emergency laparotomy for pathology consistent with inclusion into NELA
 
does not undergo emergency laparotomy
 
had review by trained surgeon
 
	
Main Exclusion Criteria:	
 
under 65 years of age
 
no surgical review
 
failed conservative management
 
	
Product, Dose, Modes of Administration:	N/A	
Duration of Treatment:	N/A	
Statistical Analysis:	Detailed later.	

#### **Background**

The work of the National Emergency Laparotomy Audit (NELA) has drastically improved the U.K. landscape for acute surgical units performing emergency laparotomies (ELAP) [1]. NELA has allowed characterisation of the ELAP population and the short and long-term outcomes have allowed each acute surgical unit to identify areas of clinical priority leading to quality improvement intervention and the development of peri-operative pathways that have improved outcomes for patients.

One successful example of a result of NELA, is the Emergency Laparotomy and Frailty Study (ELF) [2]. Frailty, a relatively new concept within the medical world, is defined as 'a medical syndrome with multiple causes and contributors that is characterised by diminished strength, endurance, and reduced physiologic function that increases an individual's vulnerability for developing increased dependency and/or death' [3].

Research so far has suggested that high frailty scores pre-operatively correlate with increased post-operative complications, length of stay, 30 and 90-day mortality and likelihood of institutionalisation (e.g. nursing home). However, the majority of these previous studies have been performed with elective rather than emergency patients [4,5]. ELF assessed the influence of frailty solely on older adults (65 years and above) undergoing ELAP finding that, independent of age, as the frailty score increased the risk of 90-mortality did too. Similar findings were reported with 30-day mortality, post-operative complications and length of critical care (High Dependency Unit or Intensive Care Unit) and overall hospital stay. The authors concluded by stating that frailty scoring provided much needed new knowledge to inform and guide older adults as they consider the implications of undergoing emergency laparotomy [6].

Despite this significant progress, there is one surgically important area that remains unknown: older patients that require, but do not undergo emergency laparotomy (NoLAP). Similar to emergency laparotomy patients before NELA started, the NoLAP population remain uncharacterised with unknown outcomes. It is not known how many patients constitute this group, what characteristics they have, what the reasons are for not undergoing surgery and what their short-term outcomes are.

There are only two published works that have reported on the NoLap population. The Perth (Australia) Emergency Laparotomy Audit prospectively collected NoLAP numbers as part of analysing ELAP patients and found them to account for only 6% of the overall population being considered for emergency laparotomy [7]. However, this small number limits characterisation of NoLAP patients and more importantly, comparison to ELAP patients. The second study prospectively recorded over three hundred patients requiring ELAP for over 14 months [8]. Patients were included according to the NELA criteria with both groups having the same data recorded. In addition, the casenotes were reviewed to ascertain the reason for the NoLAP decision. This study found NoLAPs accounted for a third of all patients (32%) requiring an ELAP with a third of these being alive at 30 days with normal admission creatinine and lactate levels increasing the likelihood of survival. This is the first work that has attempted to characterise the U.K. NoLAP population, but is limited by being both single centred and by providing limited information on the decision behind NoLAP.

We aim to apply the findings and challenges from this work into the design of this multi-centred cohort study, to definitively define the denominator.

## Aims

This study aims to:

1) Identify a U.K. consecutive series of older adults presenting with acute abdominal pathology potentially treatable by emergency laparotomy where the decision is made not to undergo surgery (NoLAP) and their associated 90-day mortality.

2) Collect, define and characterise the reasoning behind the NOLAP decision.

3) Define potential prognostic markers for mortality that could aid decision-making in the future (including frailty, NELA score and sarcopenia).

4) Compare aims 1 and 3 to those that underwent surgery (ELAP) during the same time frame as the NoLAP population.

## Outcomes

**Primary Outcome** Characterise NoLAP patient populations and document 90-day mortality.

Secondary Outcomes: Reasons for decision not to operate.

Prognostic scores: NELA score; Clinical Frailty Score.

Surgical diagnosis

Blood markers pre-operatively: lactate; C reactive protein; creatinine and WCC.

Length of critical care stay (ICU and HDU combined).

Length of hospital stay.

30-day complications

Discharge destination

30-day and 90-day mortality

Death at 1 year.

#### **Defining the Denominator Steering and Study groups**

#### Trial Management Group (TMG)

Five collaboratives form the DtD TMG: the Welsh Barbers (surgical trainees); Scottish Surgical Research Group (SSRG) (surgical trainees) and the Older Persons Surgical Outcomes Collaboration (OPSOC) which is comprised of consultant and trainee general surgeons, geriatricians, statisticians and epidemiologists interested in surgery in older people. [name] and [name] will lead the study with the former being the Chief Investigator. NELA (National Emergency Laparotomy Audit) and ELLSA (Emergency Laparoscopic and Laparotomy Scottish Audit) are the remaining collaboratives. Each collaborative will appoint one lead who will attend the TMG meetings and delegate to their own collaborative.

Both trainee collaboratives will have two mentors with experience relevant to ELF 2: [name] (lead author on U.K. NoLAP study) and [name] (NWRC and main contributor to ELF study). The training package and interpretation of sarcopenia will be led by [name] (undergraduate medical student with published experience in sarcopenia measurement) and The SSRG.

The DtD TMG will be responsible for protocol design, data handling, analysis, and dissemination of results and the preparation of manuscripts. The CI is responsible for the use of data resulting from this project. Contributing sites will register their team at the start of the study and will form the Defining the Denominator Study Group. Each site will be allowed up to 5 team members with trainees, medical students, surgical nurse practitioners, advanced nurse practitioners and nursing research staff strongly encouraged to be included.

Corporate authorship will be used for the first publication from this work (the primary aim) as described here: Welsh Barbers, SSRG, NELA, ELLSA and OPSOC on

behalf of the Defining the Denominator Study group. Each collaborator will be individually citable within their own collaborative. The CI and [name] will determine further published work. Using ELF Study as our guideline we would hope to publish at least 3 more papers.

## Study group (Local leads)

The local leads are responsible for co-ordinating and organisation of local DtD teams. The local lead will sponsor the registration of the audit and ensure that collaborators act in accordance with local clinical governance and guidelines and Good Clinical Practice. The local leads act as a link between the DtD steering group and will be responsible for the dissemination of information to local collaborators from the DtD Steering Group.

#### **Finance and Indemnity**

The DtD Study is covered by NHS Greater Glasgow and Clyde. The sponsor will be liable for negligent harm caused by the design of the trial. NHS indemnity is provided under the Clinical Negligence and Other Risks Indemnity Scheme (CNORIS).

#### Method

#### Ethics

Ethical approval will be obtained from IRAS. As per ELF, this will involve a proportionate ethical review given that this is merely an observational study and not altering patient care. Permission with be sought by the study team from the Caldicott Guardian for entry of pseudoanonymised data into REDCap (Scotland: Public Benefir and Privacy Panel for Health and Social Care, PBPP; England and Wales: Confidentiality Advisory Group).

No data will be entered from any site that has not provided such written evidence (electronically or paper). In addition, each site will be individually responsible for ensuring that all members of their team have an up to date Good Clinical Practice (GCP). REDCap will be provided and maintained by the Swansea Clinical Trials Unit.

#### **Profile of Centre**

Each site will be asked to complete a site profile questionnaire when they register. This will record the proposed site, NELA or ELLSA participation, number of ELAPs per month and names of team. In addition, each site will be asked for confirmation of their participation in the other arm of the study: sarcopenia. Each site will be asked for their radiological imaging system (e.g. PACS) and clarification of their local process of having the images transferred to the DtD Steering group to analyse.

#### **Patient Inclusion and Exclusion**

All patients 65 years or older on the date of them presenting with a condition that may be treatable by an emergency laparotomy (ELAP). Previous work suggests the majority of NoLAPs arise from the older adult population.

NoLAP patients are defined as requiring an emergency laparotomy by the responsible surgical team (trainee and/ or consultant). Such a requirement could be decided by clinical judgement and/ or radiological.

NoLAP patients must have been reviewed by a surgeon, but can be on any ward in a hospital (e.g. gynaecology).

Indication for NoLAP is exactly the same as the NELA inclusion criteria. Trauma, nonabdominal pathology excluded as per NELA (vascular, urology, gynaecology).

Patients initially requiring ELAP, but where surgical decision was made to manage conservatively will be excluded, even if that decision is subsequently changed and ELAP is performed. This includes cases where radiological drainage has failed (e.g complex diverticulitis).

#### Identification of the NOLAP

Each participating site will develop their own strategies for identifying the NoLAP patients. The DtD group has suggested highlighting to their colleagues their participation in the DtD study to ensure vigilance and accurate prospective data collection. Participation advertising material can be distributed for local promotion. Each site will be made aware that all potential patients can be recruited from any site in the hospital with particular attention being paid to record patients from non-surgical wards: e.g. ITU; HDU; gynaecology; orthopaedics; acute medical unit; geriatrics. Local teams should try to contact the surgical on-call team on a daily basis to ensure consecutive and data collection and are encouraged to review the daily emergency CT abdomen and pelvis scans list to optimise data completeness.

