#### Variables collected

The following clinical parameters will be collected for NOLAP population: age; sex; place of residence (home with no carers, home with carers, intermediate care, residential home, nursing home); ASA (American Society of Anaesthesiologists); surgical diagnosis (pre-operatively); NELA score; Clinical Frailty Score (Rockwood, 1 to 7); co-morbidities (Charlson; total number of co-morbidities); polypharmacy (5+ medications: yes/no) CT performed within 48 hours of decision (yes/ no); CT

diagnosis; date of assessment for laparotomy, time of day and location (most relevant according to the following list: general surgical ward; other surgical ward; orthopaedics; gynaecology; geriatrics; acute medical ward; other medical ward). Preoperative (within 8 hours of surgical decision) blood markers will also be recorded: lactate; C reactive protein; creatinine and WCC. The actual procedure performed will be recorded for the ELAP patients only.

For comparison to ELAP. This data will be retrieved directly from NELA and ELLSA databases with no extra data required by each participating site.

Remaining variables: length of hospital stay; length of critical care stay (ICU and HDU combined). Both groups will then be followed up for: 30-day complications (Clavien-Dindo Grading); date of discharge; discharge destination (home with no carers, home with carers, intermediate care; residential home, nursing home); 30-day and 90-day mortality and death at 1 year. Actual date of death and cause of death (1a on death certificate) will be recorded.

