# Appendix B: Proforma

Q1	Study ID	
Q2	Age at admission to study (years)	
Q3	Sex	Male Female
Q4	Comorbidities	CCF Y/N COPD Y/N
		CVA Y/N Dementia Y/N
		Hemiplegia Y/N CKD Y/N
		Leukaemia Y/N DM(complicated) Y/N
		Lymphoma Y/N DM(uncomplicated)
		Y/N
		Mild liver disease Y/N IHD Y/N
		Severe liver disease Y/N PVD Y/N
		Solid tumour Y/N Metastatic tumour
		Y/N
		AIDS Y/N
		Other:
Q5	Polypharmacy (≥5 medications)	Yes No
Q6	Place of Surgical review (choose	Emergency Department
	most relevant)	General Surgical Ward
		Other Surgical ward
		Orthopaedics
		Geriatric ward
		Acute medical ward
		Other medical ward
Q7	Care level prior to admission	Home (no carers)
		Home (with carers)
		Residential Home
		Nursing home
		Intermediate care

		Other:
Q8	Frailty score	1,2,3,4,5,6,7
Q9	NELA score	%
Q10	Interval between admission and	
	laparotomy (days)	
Q11a	Pre-decision Creatinine	
Q11b	Pre-decision CRP	
Q11c	Pre-decision WCC	
Q11d	Pre-decision Lactate	
	(all within 8 hours of decision)	
Q11	Pre-operative clinical diagnosis	
Q12	CT performed pre-operatively	Yes/ no
	(within 24 hours of decision)	
Q13	CT diagnosis	
Q14	Psoas muscle mass (TPI)	
	[TPA/ height)	
Q15	ELAP?	Yes/ no
Q16	Day of decision	Monday to Thursday
		Friday to sunday
Q17	Time of decision (24 hour)	:
Q18	Operation performed at	
	laparotomy	
Q19	Length of stay post-operative or	
	NOLAP decision (days)	
Q20	Length of critical care stay (ICU and	
	HDU) (days)	
L	l	

Q21a	Post-operative complication within 30 days	Yes	No
Q21b	Grade of complication		
Q22	Care level on discharge	Home (no carers)	
		Home (with carers)	
		Residential Home	
		Nursing home	
		Intermediate care	
		Other:	
Q23	30 day mortality	Yes	No
Q24	30 day re-admission	Yes	No
Q25	90 day mortality	Yes	No
Q26	1 year mortality	Yes	No

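### The two closed lists for place of surgical assessment disagree, and neither has a code for ITU, HDU or any other location, although sites are told to look there

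*Protocol*

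**What the plan says.** Four places in the Protocol bear on where a NoLAP patient may be found and how that place is recorded.

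- **Patient Inclusion and Exclusion.** A NoLAP patient must have been seen by a surgeon but "can be on any ward in a hospital (e.g. gynaecology").
- **Identification of the NOLAP.** Sites are to look beyond the surgical wards, with "particular attention being paid to record patients from non-surgical wards: e.g. ITU; HDU; gynaecology; orthopaedics; acute medical unit; geriatrics".
- **Variables collected.** The location of the assessment for laparotomy is to be the most relevant entry from this list: "general surgical ward; other surgical ward; orthopaedics; gynaecology; geriatrics; acute medical ward; other medical ward".
- **Appendix B: Proforma, Q6.** The item begins "Place of Surgical review (choose" and asks for the most relevant option. Its list of seven starts with "Emergency Department" and ends with "Other medical ward". It contains no ITU, HDU or gynaecology code and no free-text line. Q7 and Q22 on the same form, which record care level, do have a free-text 'other' line.

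**The concern.** The study relies on each site's own case-finding and aims at a consecutive series. The Protocol recognises that cases outside the surgical wards are easily missed and names the areas to watch. Place of assessment is the one collected item that could later show which of those areas the cases came from. If the code list leaves out areas that sites were told to search, sites must choose some other code, and different sites may choose differently for the same kind of patient.

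Two things are at stake. First, the residual ward categories would mix true ward patients with critical-care patients in proportions that depend on local habit. Second, the study could not report how many NoLAPs were found on ITU or HDU. An analysis plan cannot restore a location that the form never captured.

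**Working it through.** The Protocol gives no figure for this point, so the check is a comparison of the lists. The unit named in the case-finding text as acute medical is taken to match the acute medical ward code.

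| Location | Named for case-finding | Variables collected | Appendix B, Q6 |
|---|---|---|---|
| ITU | yes | no | no |
| HDU | yes | no | no |
| Gynaecology | yes | yes | no |
| Orthopaedics | yes | yes | yes |
| Acute medical | yes | yes | yes |
| Geriatrics | yes | yes | yes |
| Emergency Department | no | no | yes |
| General surgical | no | yes | yes |
| Other surgical | no | yes | yes |
| Other medical | no | yes | yes |
| Free-text 'other' | no | no | no |

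**Coverage of the six named areas.** The Methods list codes 4 of 6 and lacks ITU and HDU. The form codes 3 of 6 and lacks ITU, HDU and gynaecology. ITU and HDU, 2 of 6, are in neither.

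**Agreement between the lists.** Each has seven codes and six are shared. Gynaecology is only in the Methods list and Emergency Department only on the form. The union is 7 + 7 − 6 = 8 codes.

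**What happens to each patient on the form.**

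- *ITU or HDU.* No code describes the place. The nearest are the residual medical and surgical categories, and nothing tells the site which to use.
- *Gynaecology ward.* The residual surgical category is a plausible choice. However, the Methods list keeps gynaecology separate from other surgical wards, and the case-finding text counts it as non-surgical.
- *Emergency Department.* It is coded on the form, so the gap exists only in the Methods text.

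**Whether other items recover the location.** Q20 records the length of critical care stay, which may fall after the review. The section Decision-making in NoLAP Patients and Appendix A record whether intensive care took part in the decision. Neither says where the patient was when reviewed.

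**The case against.** The best defence is that the case-finding sentence is not a coding list. It tells sites where to look, by example, and a search list may reasonably be finer than a coding list. Both coding lists ask only for the most relevant entry and offer residual medical and surgical categories, so nearly every patient can be placed somewhere. A missing code excludes nobody, because eligibility extends to any ward. Critical-care involvement is also recorded elsewhere.

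Much of this stands. The gynaecology and Emergency Department points are mismatches between text and appendix, and a gynaecology patient still has a tolerable code. But the defence does not explain why two lists meant for the same variable differ, and it gives ITU and HDU no sensible code in either.

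Three stronger readings are tempting, and the documents do not support them.

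- A reader might infer that the place of the NoLAP *decision* is misreported. Q6 records the place of surgical review and the Methods text the location of assessment; neither is labelled as the place of decision.
- A reader might infer that a planned mortality comparison by location is biased. Neither Outcomes nor Data analysis names one. Location is absent from the listed outcomes, from the baseline characteristics named for description and from the adjusted model.
- A reader might want a figure for the distortion. The Protocol gives no number of critical-care NoLAPs and no mortality by location, so any such figure would rest wholly on assumed inputs.

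**Conclusion.** The point holds as a list contradiction and a coding gap. The two closed lists disagree on gynaecology and Emergency Department, and both omit ITU, HDU and an 'other' option even though ITU and HDU are named search areas. Followed as written, the variable misclassifies the place of review for critical-care patients, merges gynaecology patients into another category on the form, and cannot show the ITU or HDU yield.

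The size is small and confined to description. The number of patients affected is not stated and cannot be derived. The NoLAP proportion and overall 90-day mortality do not depend on this item. It matters because characterising the NoLAP population is a stated aim and location is one of the variables chosen for it. This is a cheap improvement and does not threaten the main results.

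The conclusion assumes that Q6 as printed is the complete list. The free-text lines that survive in Q7 and Q22 support that reading. If the live REDCap form already has the extra codes, only the Protocol text and appendix need correcting.

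**What to change.** Before data entry, adopt one list and use it both under Variables collected and in Q6. Keep the eight codes that now appear in either list:

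- Emergency Department
- General surgical ward
- Other surgical ward
- Orthopaedics
- Gynaecology
- Geriatrics
- Acute medical ward
- Other medical ward

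Add three:

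- ITU
- HDU
- Other (specify)

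That makes 8 + 3 = 11 codes. On the form it means four new options (gynaecology, ITU, HDU and other); in the Methods text, also four (Emergency Department, ITU, HDU and other). It would help to use one label for the item in both places, since one now refers to surgical review and the other to assessment for laparotomy.

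The cost is a few drop-down options and a wording change. The downside is sparser categories, which can be combined at reporting; categories merged at entry cannot be separated from this form afterwards.

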#### Variables collected

The following clinical parameters will be collected for NOLAP population: age; sex; place of residence (home with no carers, home with carers, intermediate care, residential home, nursing home); ASA (American Society of Anaesthesiologists); surgical diagnosis (pre-operatively); NELA score; Clinical Frailty Score (Rockwood, 1 to 7); co-morbidities (Charlson; total number of co-morbidities); polypharmacy (5+ medications: yes/no) CT performed within 48 hours of decision (yes/ no); CT

diagnosis; date of assessment for laparotomy, time of day and location (most relevant according to the following list: general surgical ward; other surgical ward; orthopaedics; gynaecology; geriatrics; acute medical ward; other medical ward). Preoperative (within 8 hours of surgical decision) blood markers will also be recorded: lactate; C reactive protein; creatinine and WCC. The actual procedure performed will be recorded for the ELAP patients only.

For comparison to ELAP. This data will be retrieved directly from NELA and ELLSA databases with no extra data required by each participating site.

Remaining variables: length of hospital stay; length of critical care stay (ICU and HDU combined). Both groups will then be followed up for: 30-day complications (Clavien-Dindo Grading); date of discharge; discharge destination (home with no carers, home with carers, intermediate care; residential home, nursing home); 30-day and 90-day mortality and death at 1 year. Actual date of death and cause of death (1a on death certificate) will be recorded.

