# Q21a. Clavien-Dindo Classification of Surgical Complications

Clavien-Dindo Classification of Surgical Complications	
Grade I	Any deviation from the normal postoperative course without the need for pharmacological treatment or surgical, endoscopic, and radiological interventions. Allowed therapeutic regimens are: drugs such as antiemetics, antipyretics, analgetics, diuretics, electrolytes, and physiotherapy. This grade also includes wound infections opened at the bedside.
Grade II	Requiring pharmacological treatment with drugs other than allowed for grade I complications. Blood transfusions and total parenteral nutrition are also included.
Grade IIIa	Surgical, endoscopic, or radiological intervention that is not under general anesthesia
Grade IIIb	Surgical, endoscopic, or radiological intervention that is under general anesthesia
Grade IVa	Life-threatening complication requiring intermediate care or intensive care unit management, single organ dysfunction (including dialysis, brain hemorrhage, ischemic stroke, and subarrachnoidal bleeding)
Grade IVb	Life-threatening complication requiring intermediate care or intensive care unit management, multi-organ dysfunction (including dialysis)
Grade V	Death of a patient
Suffix "d"	If the patient suffers from a complication at the time of discharge, the suffix "d" (for "disability") is added to the respective grade of complication. This label indicates the need for a follow-up to fully evaluate the complication

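### The 30-day complication item is worded for operated patients only, so the Clavien-Dindo outcome is undefined for NoLAP patients who survive and dominated by deaths otherwise

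*Protocol*

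**What the plan says.** - **Who is followed.** Variables collected applies the follow-up item "30-day complications (Clavien-Dindo Grading") to both groups. Outcomes lists 30-day complications among the secondary outcomes without limiting them to one group.
- **Who the NoLAP patients are.** The Study Synopsis includes a patient who "does not undergo emergency laparotomy".
- **What the form asks.** Appendix B, Q21a, is a Yes/No item headed "Post-operative complication within 30 days". Q21b then asks for the grade. Neither has a not-applicable code or NoLAP wording.
- **What the neighbouring item asks.** Q19 begins "Length of stay post-operative or" and goes on to name the NoLAP decision as the alternative starting point.
- **How the scale is defined.** In the definitions for Q21a, Grade I starts from "Any deviation from the normal postoperative course". Grade II is "Requiring pharmacological treatment with drugs other than allowed for grade I complications". Grades III and IV rest on an intervention, or on organ dysfunction managed in intermediate or intensive care. Grade V is death.
- **How it is analysed.** Data analysis says that complications will be described. The only NoLAP versus ELAP model there is for 90-day mortality. Aim 4 carries aims 1 and 3 over to ELAP, and neither names complications.

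**The concern.** A listed secondary outcome is collected in the study's main population with an item that presupposes an operation this population did not have. A site that takes the wording literally has to answer No for a NoLAP patient. Another site may grade the course of the untreated disease. Both follow the form, and the protocol does not choose between them.

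The grades also shift in meaning without an operation (inference from the scale's definitions). Drug treatment of the presenting pathology could be coded Grade II although nothing new has happened. Grade IV depends on critical care being given, yet Appendix A records intensive-care reasons for not operating and whether a DNACPR order is in place. Organ failure in such a patient may therefore never be graded IV.

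At stake is whether the NoLAP complication rate, part of characterising the group, can be interpreted. Readers will also set it beside the ELAP rate, because the same scale is collected in both groups.

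**Working it through.** The protocol gives no figure for complications, so there is none to reproduce. The check sets the items side by side and then asks how far deaths would determine the NoLAP grades.

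**Step 1: fit of the items to NoLAP.**

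| Item | Start point or reference | Works without an operation? |
|---|---|---|
| Q19 length of stay | Operation or NoLAP decision | Yes |
| Q21a complication | Postoperative only | No |
| Grade I | Normal postoperative course | No |
| Grades II to IV | Treatment, intervention or organ dysfunction | Can be assigned, but not separated from treatment of the presenting disease |
| Grade V | Death | Yes, but repeats 30-day mortality (Q23) |

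Q19 was adapted to NoLAP and Q21a was not.

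**Step 2: inputs.**
- m = proportion dead by day 30 (Grade V). NoLAP: a third alive at 30 days in the single-centre study in Background, so m = 1 − 1/3 = 2/3. ELAP: 20% mortality at 90 days in the earlier frailty study (Patient numbers and power calculation), used as an upper limit for day 30.
- q = proportion of survivors with a Grade I to IV event. The protocol gives no value, so q is varied from 0 to 1.

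**Step 3: formulas.** Any-grade rate = m + (1 − m)q. Grade V share of graded patients = m / [m + (1 − m)q]. The denominator cannot exceed 1, so the share is never below m.

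**Step 4: results.**

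| q | NoLAP any grade | NoLAP Grade V share | ELAP any grade | ELAP Grade V share |
|---|---|---|---|---|
| 0 | 67% | 100% | 20% | 100% |
| 0.25 | 75% | 89% | 40% | 50% |
| 0.5 | 83% | 80% | 60% | 33% |
| 0.75 | 92% | 73% | 80% | 25% |
| 1 | 100% | 67% | 100% | 20% |

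Example, NoLAP at q = 0.5: 0.667 + 0.333 × 0.5 = 0.833, and 0.667 / 0.833 = 0.80.

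**Step 5: effect of how sites read the item.** If Q21a is answered No for every NoLAP patient, deaths included, the any-grade rate is 0%. If only deaths are graded, it is 67%. If survivors are graded too, it lies between 67% and 100%. The same patients can yield any of these under the present wording.

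**Step 6: direction of any apparent difference.** Where NoLAP deaths are graded, the NoLAP rate is at least 67%. ELAP reaches that level only if 0.20 + 0.80q = 0.667, that is q = 0.467 / 0.80 = 0.58. The direction therefore depends on an unstated survivor rate and on how deaths are entered.

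**The case against.** **No comparison of complications is planned.** This stands. The protocol collects complications in both groups and describes them. A reader might infer a planned NoLAP versus ELAP contrast, but neither Data analysis nor Aims contains one. What remains is that the descriptive NoLAP rate is itself undefined.

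**Grades II to IV can occur without surgery.** This also stands. A reader might infer that the outcome merely restates mortality, or that surviving NoLAP patients cannot be graded at all. The scale does not support either. The any-grade contrast equals the mortality contrast only if q = 0 in both groups, which nothing in the protocol says. The supportable statement is that deaths dominate and the remaining grades lack a definition.

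**The direction of bias is not shown.** This stands too. A reader might infer that NoLAP patients would appear to have fewer complications. With deaths graded, they could equally appear to have more (step 6).

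**Training or the SAP could settle it.** Training Materials promises online instruction on completing the form, so different readings by site are a risk and not a certainty. The content of that training is not shown. A SAP can choose how to summarise grades, but it cannot recover answers already recorded under different readings of Q21a.

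**The size rests on one study.** Background itself calls that study limited because it is single-centred. If NoLAP mortality is lower, the dominance of Grade V falls with it, since the minimum share equals m. The missing definition does not depend on m.

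**Conclusion.** The point holds as a defect of definition. The 30-day complication outcome is assigned to both groups, but its form item and its lowest grade presuppose an operation, and no event definition or start point is given for NoLAP. Grades among NoLAP survivors would be absent or inconsistent. Grade V would account for at least two thirds of graded NoLAP patients if deaths are graded and 30-day mortality is as in the cited single-centre study. For ELAP the corresponding share is at most 50% once a quarter or more of survivors have an event, taking 20% as the upper limit for 30-day deaths.

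The described rates would then be uninterpretable for NoLAP and could not be read beside those for ELAP. The primary outcome and the 90-day mortality model are untouched, so the severity is low.

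**What to change.** **Preferred change.**
1. Reword Q21a along the lines of Q19: complication within 30 days of operation or of the NoLAP decision.
2. State in the definitions that for NoLAP patients only new events after the decision count, and that treatment of the presenting pathology does not.
3. In Data analysis, report Grade V separately from Grades I to IV, so that deaths are not counted again as complications.

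The cost is a small form change and a few sentences of definition. It should be in place before data entry, because recorded answers cannot be reinterpreted later.

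**Alternative.** If the team does not want NoLAP morbidity, code Q21a and Q21b as not applicable for NoLAP and amend the statement in Variables collected that both groups are followed for complications. This loses morbidity data on the group the study sets out to characterise. It would also leave sites little use for the item, because the same section says ELAP data come from the national audit databases without extra entry by sites.
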